#### 3.3.1. Risk/Benefit for Dupilumab

Dupilumab has shown clinically relevant benefit in several type 2-mediated immune disorders including AD, bronchial asthma, CRSwNP, and eosinophilic esophagitis (EoE).

In adults and adolescents with moderate-to-severe uncontrolled asthma, dupilumab significantly reduced the risk of severe exacerbations compared to placebo and consistently improved lung function (FEV1), asthma control, and HRQoL in patients with a type 2 inflammatory signature as evidenced by a blood eosinophil count of  $\geq$ 150 cells/µL or a fractional exhaled nitric oxide concentration of  $\geq$ 25 parts per billion (ppb). In OCS-dependent patients with severe asthma, dupilumab significantly reduced the need for OCS by ~70% while at the same time reducing asthma exacerbations and improving FEV1 compared to placebo.

Type 2 inflammation plays a critical role in the pathogenesis of ABPA. The hypothesis that blocking key mediators of type 2 inflammation will lead to clinical benefit in patients with ABPA is supported by a post-hoc subgroup analysis from the completed dupilumab phase 3 pivotal study EFC13579 (QUEST) in patients with moderate-to-severe asthma who met the suggested criteria for ABPA diagnosis at baseline. The results from a total of 30 patients (n=18 in the combined dupilumab group and 12 in the combined placebo group) provide compelling clinical evidence for the efficacy of dupilumab in patients with ABPA. Dupilumab treatment compared to placebo showed an approximately 80% reduction in annualized severe exacerbation events and a 0.26L improvement in change from baseline to week 24 in pre-bronchodilator (BD) FEV1. In clinical practice, serum total IgE, which is elevated in patients with ABPA, is monitored to assess ABPA disease activity. Dupilumab suppressed serum total IgE by approximately 70% from baseline over a 52-week treatment period. Overall, dupilumab was well tolerated in this subgroup of patients with ABPA.

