#### 10.2.2. Serious Adverse Event

An SAE is any untoward medical occurrence that at any dose:

- Results in **death** includes all deaths, even those that appear to be completely unrelated to study drug (eg, a car accident in which a patient is a passenger).
- Is **life-threatening** in the view of the investigator, the patient is at immediate risk of death at the time of the event. This does not include an AE that had it occurred in a more severe form, might have caused death.
- Requires in-patient **hospitalization** or **prolongation of existing hospitalization**. In-patient hospitalization is defined as a hospital admission (any duration) or an emergency room visit for longer than 24 hours. Prolongation of existing hospitalization is defined as a hospital stay that is longer than was originally anticipated for the event, or is prolonged due to the development of a new AE as determined by the investigator or treating physician.
- Results in persistent or significant **disability/incapacity** (substantial disruption of one's ability to conduct normal life functions).
- Is a congenital anomaly/birth defect
- Is an **important medical event**. Important medical events may not be immediately lifethreatening or result in death or hospitalization, but may jeopardize the patient or may require intervention to prevent one of the other serious outcomes listed above (eg, intensive treatment in an emergency room or at home for allergic bronchospasm; blood dyscrasias or convulsions that do not result in hospitalization; or development of drug dependency or drug abuse).

Criteria for reporting SAEs must be followed for these events.

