## 11.4.5.1. Adverse Events

## **Definitions**

For safety variables, 3 observation periods are defined:

- The pre-treatment period is defined as the time from signing the ICF to prior to the first dose of study drug.
- The on-treatment period is defined as the time from day 1 (on or after administration of the first dose of study drug) to the date of last dose of study drug +14 days or the date of patient last contact, whichever is earlier
- The follow-up period is defined as the time from the date of last dose of study drug +15 days to the EOS visit or the date of patient last contact, whichever is earlier

The treatment-emergent period is comprised of the on-treatment and follow-up periods.

Treatment-emergent adverse events are defined as those that are not present at baseline or represent the exacerbation of a pre-existing condition during the treatment-emergent period.

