7.1.2. Severe Respiratory Exacerbations

Occurrences of severe respiratory exacerbations are recorded during the entirety of the study duration (i.e., from screening through post-treatment follow-up). A severe respiratory exacerbation is defined as new onset of symptoms or clinical worsening of respiratory symptoms requiring systemic corticosteroid treatment for ≥ 3 consecutive days; for patients who are on maintenance systemic corticosteroids, at least double the dose of maintenance systemic corticosteroids for ≥ 3 consecutive days (with or without antibiotic therapy if indicated). Per protocol, the start dates of severe respiratory exacerbation events must occur ≥ 28 days apart to be considered as distinct events. A secondary efficacy endpoint is the annualized rate of severe respiratory exacerbations over the 24-52-week treatment period.

Another secondary efficacy endpoint is the annualized rate of ABPA-related exacerbations over the 24-52-week treatment period. ABPA-related exacerbations are defined as severe respiratory exacerbations (as defined above) that are associated with a doubling of serum total IgE from the prior pre-exacerbation value. Per protocol, patients who experience a severe respiratory exacerbation will have, as soon as possible, an unscheduled visit at the site for the collection of a blood sample for serum total IgE measurement. The serum total IgE value from this unscheduled visit (or the next available measurement if the unscheduled visit was not performed or if the blood draw from the unscheduled visit did not result) will be used to determine if a doubling of the serum total IgE from the prior pre-exacerbation value occurred. Only serum total IgE measurements collected within 30 days after the severe respiratory exacerbation (i.e., with date of serum total IgE blood draw – start date of severe respiratory exacerbation event + 1 ≤ 30) will be considered valid for the purposes of determining whether a doubling of serum total IgE occurred. If the serum total IgE measurement is collected beyond 30 days after the severe respiratory exacerbation event or if no post-exacerbation serum total IgE measurement is available, the severe respiratory exacerbation will be considered to be not ABPA-related for the purposes of analysis. The pre-exacerbation value is defined as the value of the most recent IgE measurement collected prior to the start date/time of the severe respiratory exacerbation event.

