The annualized rate of severe respiratory exacerbations requiring either hospitalization or observation for >24 hours in an ED/urgent care facility over the 24-52-week treatment period is also a secondary efficacy endpoint.

For each of the aforementioned respiratory exacerbation efficacy endpoints, severe respiratory exacerbations will be determined based on the information entered in the Adverse Event eCRF. Specifically, adverse event records with verbatim term that includes the text “severe respiratory exacerbation” will be selected for analysis. To determine whether a severe respiratory exacerbation is ABPA-related, the date/time of each severe respiratory exacerbation event recorded on the Adverse Event eCRF will be used to identify the prior and subsequent serum total IgE measurements. To determine, whether a severe respiratory exacerbation event required hospitalization or observation for >24 hours in an ED/urgent care facility, the information entered in the “Comment” field on the Adverse Event eCRF will be used; sites will enter the text “HEDURG: Yes” into the comment field to indicate severe respiratory exacerbations requiring hospitalization or observation for >24 hours in an ED/urgent care facility, as instructed in the Clinical Completion Guidelines (CCGs).

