10.1. Adverse Events

All new or worsening AEs occurring from the time of signing of the ICF through the end of the study will be recorded and coded using the MedDRA® dictionary. The definitions of AEs, serious adverse events (SAEs), and adverse events of special interest (AESIs) are provided in Sections 10.2.1-10.2.3 of the protocol.

Pre-treatment AEs and TEAEs are defined as follows:

- Pre-treatment AEs are AEs that developed or worsened in severity during the pre-treatment period, as defined above.
- TEAEs are AEs that developed or worsened in severity compared to baseline during the on-treatment and follow-up periods, as defined above. As only new AEs that were not present at baseline and pre-existing AEs that worsen during the on-treatment and follow-up periods will be summarized in this study, all AEs collected during the on-treatment and follow-up periods are considered TEAEs.

Adverse events will be summarized with incidence tables. Adverse event incidence tables will present the number and percentage of patients experiencing an AE within each treatment group, sorted by decreasing frequency of SOC and PT in the dupilumab treatment group. Multiple occurrences of the same event in a patient will only be counted once in the summaries. For tables showing AE severity, if a patient has multiple occurrences of the same PT or SOC, only the worst severity will be counted in the summary.

AE summaries will be presented for the TEAEs. The following summaries for TEAEs will be presented by treatment group:

- Overview of TEAEs, consisting of the number and percentage of participants with any TEAE, with any drug-related TEAE, with any TEAE leading to permanent discontinuation of study drug, with any TEAE resulting in death, with any treatment-emergent SAE, with any treatment-emergent, drug-related SAE, and with any treatment-emergent SAE leading to permanent discontinuation of study drug.
- TEAEs by primary SOC and PT
- TEAEs by primary SOC, high level term (HLT), and PT
- TEAEs by primary SOC, PT, and severity (according to the grading scale in Section 10.2.4 of the protocol)
- TEAEs by primary SOC and PT that occur in $\geq 5\%$ of patients in either treatment group
- TEAEs related to study drug by primary SOC and PT
- Injection site reaction TEAEs by primary SOC, HLT, and PT
- TEAEs with fatal outcome by primary SOC and PT
- Serious TEAEs by primary SOC and PT
- TEAEs leading to permanent discontinuation of study treatment by primary SOC and PT

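### Severe exacerbations, an efficacy outcome, also count in the pooled TEAE and SAE rows, and no planned table gives the number of patients with a TEAE other than an exacerbation

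*SAP*

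**What the plan says.** SAP 7.1.2 gives the outcome an efficacy role: "A secondary efficacy endpoint is the annualized rate of severe respiratory exacerbations over the 24-52-week treatment period". For this endpoint, and for the ABPA-related and hospital/emergency variants, "severe respiratory exacerbations will be determined based on the information entered in the Adverse Event eCRF". The rule selects "adverse event records with verbatim term that includes the text" severe respiratory exacerbation. A comment-field flag identifies those needing admission or more than 24 hours of observation.

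The safety sections make no exception for these records. SAP 10.1 says that "all AEs collected during the on-treatment and follow-up periods are considered TEAEs". Protocol 11.4.5.1 points the same way: "Treatment-emergent adverse events are defined as those that are not present at baseline or represent the exacerbation of a pre-existing condition". The first planned table in SAP 10.1 is an "Overview of TEAEs, consisting of the number and percentage of participants with any TEAE", with further rows that include any treatment-emergent SAE. TEAEs by organ class and preferred term, by severity, and serious TEAEs follow.

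On seriousness, Protocol 10.2.2 states: "In-patient hospitalization is defined as a hospital admission (any duration) or an emergency room visit for longer than 24 hours". Exacerbations that meet the hospital/emergency endpoint will therefore largely be SAEs too.

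TEAE incidence is secondary endpoint 10 (Protocol 4.1.2), and SAP 10 provides on-treatment tables specifically to support it. Protocol 3.3.1 reports an "approximately 80% reduction in annualized severe exacerbation events" on dupilumab in a post-hoc subgroup of 30 patients (18 versus 12).

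**The concern.** If dupilumab prevents exacerbations, the pooled adverse event rows fall on dupilumab for that reason alone. The any-TEAE row, read as a summary of tolerability, would then contain part of the efficacy result, and a real excess of other events would look smaller than it is.

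The preferred-term rows do not repair this. A patient can appear under several terms, so the number of patients with at least one TEAE other than an exacerbation cannot be worked out from them. Exacerbations are also selected by verbatim text but tabulated by coded term, and the SAP does not say which terms they code to. A term row therefore need not match the endpoint events.

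At stake is the descriptive comparison of tolerability. Protocol 3.1 hypothesises that dupilumab will be well tolerated compared with placebo.

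**Working it through.** The documents give no TEAE figure to reproduce. Their only design calculation is the power for FEV1, which does not bear on this point.

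**Inputs from the documents**
- Exacerbations in up to 24% to 50% of patients each year (Protocol 1), read here as the yearly risk of at least one.
- 80% lower rate on dupilumab (Protocol 3.3.1).
- Treatment for 24 to 52 weeks, about 30 patients per arm.

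**Assumptions**
- Mean treatment time of 40 weeks, so T = 40/52 = 0.769 years. The 12-week follow-up is not modelled.
- Other TEAEs in 60% on placebo and 75% on dupilumab, a true excess of 15 points.
- Exacerbations independent of other TEAEs.
- Constant rate within each arm (Poisson).

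**Formulas**
- Yearly rate r = −ln(1 − yearly risk): 0.274 for 24% and 0.693 for 50%.
- Risk of at least one exacerbation: e = 1 − exp(−rT) on placebo, 1 − exp(−0.2rT) on dupilumab.
- Any TEAE = 1 − (1 − e)(1 − q), where q is the risk of another TEAE.

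**Unequal other harms (q = 60% versus 75%)**

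| Placebo exacerbations | e, placebo / dupilumab | Any TEAE, placebo | Any TEAE, dupilumab | Dupilumab minus placebo |
|---|---|---|---|---|
| 24% per year | 0.190 / 0.041 | 1 − 0.810 × 0.40 = 67.6% | 1 − 0.959 × 0.25 = 76.0% | +8.4 points |
| 50% per year | 0.413 / 0.101 | 1 − 0.587 × 0.40 = 76.5% | 1 − 0.899 × 0.25 = 77.5% | +1.0 point |
| 1.0 event/year (assumed) | 0.537 / 0.143 | 81.5% | 78.6% | −2.9 points |
| 1.5 events/year (assumed) | 0.685 / 0.206 | 87.4% | 80.2% | −7.2 points |

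At the protocol's own frequencies the excess is attenuated but keeps its sign. It reverses in the last two rows, whose rates are not in the documents.

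**Equal other harms (q = 60% in both arms)**
- 24% per year: 67.6% versus 1 − 0.959 × 0.40 = 61.7%, about 6 points in dupilumab's favour.
- 50% per year: 76.5% versus 1 − 0.899 × 0.40 = 64.0%, about 12 points in its favour.

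**Sensitivity**
- With no effect on exacerbations, e is the same in both arms and an equal any-TEAE row hides no excess.
- SAP 7.2.2 models these counts as negative binomial. With an assumed dispersion of 1, e = 1 − 1/(1 + rT) on placebo, and the dupilumab risk uses 0.2rT. Other TEAEs at 60% versus 75% then give 77% versus 78% at 1.0 event per year, and 81% versus 80% at 1.5. Overdispersion nearly removes the reversal.

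**Any-SAE row**
The documents give neither the serious share of exacerbations nor the risk of other SAEs. Assume 52 weeks, a 5% risk of other SAEs on placebo, and 10% to 50% of exacerbations serious. Solving the same formula for equal any-SAE rows gives a concealed dupilumab excess of 2 to 10 points at 24% per year, or 5 to 23 points at 50%.

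**The case against.** Counting exacerbations as TEAEs follows the protocol's definition, so the plan contains no error or contradiction. Safety is descriptive, with no test planned. A 3- to 7-point gap is one or two patients of 30, against a standard error near 10 points (√(2 × 0.8 × 0.2/30) = 0.103), so the overview row could not settle tolerability either way. All of this stands, and it limits the weight of the point.

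A reader might infer that every TEAE and SAE summary is contaminated. The documents do not support that. Injection-site reactions (SAP 10.1), adverse events of special interest (SAP 10.1.1), and COVID-19 and conjunctivitis events (SAP 10.5) are restricted by search term and would not normally contain exacerbations. Drug-related and discontinuation rows include an exacerbation only if it was judged related or led to stopping. Any organ class to which exacerbations do not code is already a patient-level count free of them. Protocol 11.4.5.1 also plans a listing of deaths and other SAEs, from which patients with a serious event other than an exacerbation can be counted.

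These answers do not reach the any-TEAE row or the affected organ-class totals. No planned output gives the patient count without exacerbations there.

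**Conclusion.** The point holds for the pooled rows: any TEAE, any treatment-emergent SAE, and the totals of organ classes to which exacerbations code. These mix efficacy with tolerability, and no planned table separates the two.

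A reader might go further and expect the overview to turn a true excess of other harms into an apparent benefit. The documents do not show that. At the protocol's 24% to 50% per year the result is attenuation. Reversal needs something like the assumed 1.0 to 1.5 events per year. Inclusion criterion 5 enriches for patients with a recent severe exacerbation or chronic corticosteroid use, which may or may not produce such rates.

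The sizes are illustrative. They rest on a literature frequency quoted as an upper range, a reduction seen in a small post-hoc subgroup, assumed risks of other events, and independence. This is a modest reporting weakness in the safety comparison and does not affect the primary FEV1 analysis.

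**What to change.** In SAP 10.1, keep every planned table. Repeat three of them (the TEAE overview, serious TEAEs, and TEAEs by organ class and preferred term) after removing all adverse event records that the verbatim-term rule in SAP 7.1.2 selects. State that removal includes matched records starting less than 28 days apart, which the endpoint does not count as distinct events. Describe tolerability from both versions.

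The cost is a short SAP addition and three repeat tables built on a selection the SAP already makes. No new data are needed. One limit should be footnoted: disease worsening recorded under different wording stays in the repeat tables.

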7.1.3. ACQ-5 Score

[figure not shown]
The ACQ-5 score is calculated for each patient at each time point of administration as the mean of the first 5 questions on the ACQ patient-reported outcome (PRO) instrument; the ACQ-5 is administered at screening, baseline, Weeks 2, 4, 8, 12, 24, 36, 44, and at EOT and EOS. For patients receiving OCS at baseline, the ACQ-5 is also administered at Weeks 6, 10, 14, and 16 when these visits are performed in-clinic. A secondary PRO endpoint is the absolute change from baseline in the ACQ-5 score over the 24-52-week treatment period.

[figure not shown]
7.1.4. SGRQ Total Score

The SGRQ PRO instrument is administered at baseline, Weeks 4, 12, 24, 36, and at EOT and EOS. Derivation of the total score for each patient at each time point of administration is described in Appendix 14.5. A secondary PRO endpoint is the absolute change from baseline in the SGRQ total score over the 24-52-week treatment period.

The proportion of participants achieving a reduction in the SGRQ total score of ≥ 4 points from baseline at Weeks 12, 24, 36, and 52 will also be assessed as a secondary PRO endpoint.

7.1.5. Corticosteroid Dose

7.1.6. Pre- and Post-bronchodilator Lung Function Parameters

Pre-bronchodilator lung function parameters including [REDACTED] are collected at screening, baseline, Weeks 2, 4, 8, 12, 24, 36, 44, and at EOT and EOS. These parameters are also collected for patients on OCS at baseline at Weeks 6, 10, 14, and 16 when these visits are performed in-clinic. [REDACTED]
[REDACTED]
[REDACTED]
[REDACTED]
[REDACTED]
[REDACTED]
[REDACTED]
[REDACTED]

7.1.7. Oral Antifungal Use

For patients who are not on oral antifungals at baseline, if 2 or more exacerbations occur during the treatment period, a patient may be initiated on antifungal therapy at the investigator's discretion.

[REDACTED]
[REDACTED]
[REDACTED]
[REDACTED]
[REDACTED]
[REDACTED]
[REDACTED]
[REDACTED]
[REDACTED]
[REDACTED]

7.1.8. Hospitalizations

Any AEs requiring hospitalization will be recorded on the Adverse Event eCRF. [REDACTED]
[REDACTED]

7.1.9. [REDACTED]

[REDACTED]

[REDACTED]

[REDACTED]

7.1.10. [REDACTED]

[REDACTED]

[REDACTED]

[REDACTED]

[REDACTED]

[REDACTED]

[REDACTED]

7.1.11. Biomarkers

Serum total IgE is collected at screening, baseline, Weeks 4, 8, 12, 24, 36, and at EOT and EOS. Serum *A fumigatus*-specific IgE is collected at screening, baseline, Weeks 4, 12, 24, 36, and at EOT and EOS. Secondary biomarker endpoints include the percent change from baseline in serum total IgE over the 24-52-week treatment period and the percent change from baseline in serum *A fumigatus*-specific IgE over the 24-52-week treatment period.

FeNO is collected at screening, baseline, Weeks 4, 8, 12, 24, 36, 44, and at EOT and EOS. A secondary biomarker endpoint is the percent and absolute change from baseline in FeNO over the 24-52-week treatment period.

[REDACTED]

[REDACTED]

[REDACTED]

[REDACTED]

7.1.12. Gene Expression

Patients who are not on chronic systemic steroids and not on antifungal therapy at baseline who provide written informed consent will be eligible to participate in the blood immunophenotyping substudy. Blood samples for the immunophenotyping substudy are drawn at baseline, Week 4, Week 12, and at EOT. [REDACTED]

[REDACTED]

[REDACTED]

[figure not shown]
7.2. Analysis of Efficacy Data

7.2.1. Analysis of Pre-bronchodilator FEV1

The absolute change from baseline in pre-bronchodilator FEV1 at Week 24 will be analyzed using a mixed-effects model with repeated measures (MMRM) approach. The vector of responses will consist of the absolute change from baseline in pre-bronchodilator FEV1 at Weeks 2, 4, 8, 12, and 24. As only patients on OCS at baseline will have pre-bronchodilator FEV1 measured at Weeks 6, 10, 14, and 16 (when these visits are performed in-clinic), these time points will not be included in the response vector in the MMRM model to prevent introduction of any potential bias. For patients who discontinue study treatment prior to Week 24, any off-study treatment pre-bronchodilator FEV1 values collected after the discontinuation of study treatment through Week 24 will be included in the analysis. The MMRM model will include OCS use at screening, OAF use at screening, region, age at screening, sex, height at screening, baseline eosinophil count, treatment, visit, treatment-by-visit interaction, baseline pre-bronchodilator FEV1 value, and baseline pre-bronchodilator FEV1 value-by-visit interaction as covariates. An unstructured covariance matrix will be used to model the correlations between repeated measurements. If this model does not converge, the covariance structure will be modified and additional models run until convergence is achieved. If additional models are needed, the order of the covariance structures will be as follows: heterogeneous autoregressive(1), autoregressive(1), and compound symmetry.

Parameters will be estimated using the restricted maximum likelihood (REML) method and the Newton-Raphson algorithm. Statistical inference for the treatment comparison of the absolute change from baseline in pre-bronchodilator FEV1 at Week 24 will be derived from the MMRM model using the Kenward Roger method for calculation of the denominator degrees of freedom for the tests of the fixed effects. The point estimate, 2-sided 95% CI, and p-value for the treatment comparison will be provided. [REDACTED]

[REDACTED]

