2.2. Sample Size and Power Considerations

The power calculation for this study is based on a comparison between dupilumab 300 mg Q2W and placebo with regard to the primary efficacy endpoint of the absolute change from baseline in pre-bronchodilator FEV1 at Week 24. Assuming a 1:1 randomization ratio, a standard deviation (SD) for the change from baseline in pre-bronchodilator FEV1 at Week 24 of [REDACTED] in both groups, a 2-sided Type 1 error of 0.05, and a dropout rate of [REDACTED] by Week 24, with approximately 60 randomized patients (\approx 30 per group), the study will have approximately 96% power to detect a difference of [REDACTED] in the change from baseline in pre-bronchodilator FEV1 at Week 24 between the dupilumab and placebo groups. The power was calculated via a 2-sample t-test using [REDACTED] software.

[REDACTED]

[REDACTED]

[REDACTED]

[REDACTED]

[REDACTED]

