Unless otherwise specified, statistical testing will be performed using 2-sided tests with a nominal Type 1 error of 0.05. Two-sided confidence intervals (CIs) will be at the nominal 95% level unless otherwise specified.

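### The last two covariance fallbacks for the primary FEV1 model assume equal variance across visits; if they are ever reached, the Week 24 test can miss its 5% level

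*SAP*

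**What the plan says.** The primary analysis (SAP Section 7.2.1) is an MMRM of the change in pre-bronchodilator FEV1 at Weeks 2, 4, 8, 12 and 24. It uses REML, an unstructured covariance and Kenward-Roger degrees of freedom, and the treatment comparison is read at Week 24. The only trigger for a fallback is non-convergence. The replacement structures are, in order, "heterogeneous autoregressive(1), autoregressive(1), and compound symmetry". The visible text has no empirical (sandwich) variance and no step for failure of compound symmetry. Some text after the inference paragraph is blacked out.

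SAP Section 7 sets the level: "statistical testing will be performed using 2-sided tests with a nominal Type 1 error of 0.05". Protocol Section 11.4.3 names a different covariance structure or fewer covariates as possible remedies and leaves the details to the SAP, so the SAP list is the operative rule.

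The only SD mentioned is for Week 24 (SAP Section 2.2): "a standard deviation (SD) for the change from baseline in pre-bronchodilator FEV1 at Week 24 of [REDACTED] in both groups". No visit-specific variability appears in the visible text of either document.

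**The concern.** Heterogeneous AR(1) estimates a separate variance for each visit. Homogeneous AR(1) and compound symmetry estimate a single variance for all five. If the Week 24 residual variance is above the average over visits, these two structures make the Week 24 standard error too small and the test anti-conservative. If it is below the average, the test is conservative. Kenward-Roger corrects for small samples, not for a wrong covariance structure.

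The design gives some reasons why variability could rise by Week 24. OCS tapering starts 4 weeks after randomization (Protocol Section 8.2), and values after rescue, prohibited medication or treatment discontinuation stay in the analysis (SAP Section 7.2.1.1). These make growth plausible but do not establish its size. At stake is the level of the trial's only formal hypothesis test, on a path that is written into the plan.

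**Working it through.** **The plan's own figure.** The documents state no type I error under a fallback, only the nominal 0.05. The one design figure is the power: "the study will have approximately 96% power to detect a difference of" a redacted difference, "with approximately 60 randomized patients" split 1:1. The SD, the difference and the dropout rate ("a dropout rate of [REDACTED] by Week 24") are redacted, so the 96% can be neither confirmed nor refuted. By the two-sample t-test it implies difference/SD = 0.974 at 30 per arm, or 1.029 at 27 per arm (10% dropout, assumed). The point below does not depend on it.

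**Inputs.** From the SAP: two-sided alpha 0.05 (Section 7), about 60 patients at 1:1 (Section 2.2), five visits, the covariates and the fallback order (Section 7.2.1), and region pooled to two levels (Section 11.5). Assumed: the path of the SD over visits, the correlation pattern, and dropout of 0% or 10%.

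**Closed form.** Under an equal-variance structure the Week 24 standard error uses roughly the mean variance over the five visits. With k = (Week 24 variance)/(mean variance),

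alpha ≈ 2 × [1 − Φ(1.96/√k)].

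Worked case, SD rising 1.5-fold in equal steps by visit (1, 1.125, 1.25, 1.375, 1.5):
- mean variance = (1 + 1.266 + 1.563 + 1.891 + 2.25)/5 = 1.594
- k = 2.25/1.594 = 1.412, √k = 1.188
- alpha ≈ 2 × [1 − Φ(1.650)] = 9.9%.

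Two paths in litres (assumed):
- 0.30, 0.32, 0.34, 0.36, 0.40: mean variance 0.1195, k = 0.16/0.1195 = 1.339, √k = 1.157, alpha ≈ 9.0%.
- 0.25, 0.28, 0.30, 0.33, 0.40: mean variance 0.1000, k = 0.16/0.1000 = 1.60, √k = 1.265, alpha ≈ 12.1%.

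A simulation of these two paths (20,000 null trials, 30 per arm, correlation 0.7, complete data) gave 9.0% and 11.8% with the pooled variance, 4.9% with constant SD, and 5.1-5.2% with a Week 24-specific variance.

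**Model-based check.** The SAP model was fitted by REML with AR(1) and with compound symmetry. There were 60 patients and 22 fixed-effect parameters: 7 baseline covariates, plus 5 each for visit, treatment by visit and baseline FEV1 by visit. Three true correlation patterns were used, with 2,000 null trials per scenario (Monte Carlo SE about 0.5-0.7 points). Satterthwaite degrees of freedom stood in for Kenward-Roger.

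| SD at Week 24 / Week 2 | Closed form, linear by visit | Closed form, linear by week | REML simulation, AR(1) and CS |
|---|---|---|---|
| 1.0 | 5.0% | 5.0% | 5.3-6.4% |
| 1.2 | 7.2% | 7.9% | 7.4-8.5% |
| 1.3 | 8.2% | 9.3% | not run |
| 1.5 | 9.9% | 11.8% | 9.2-10.9% |
| 1.75 | 11.7% | 14.5% | 11.1-12.6% |
| 2.0 | 13.1% | 16.7% | 12.2-13.8% |

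The simulation used SDs linear by visit. So 9-12% corresponds to growth of about 1.5- to 1.75-fold if linear by visit, or about 1.3- to 1.5-fold if linear by week.

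**Falling SD.** For a linear fall from 1.25 to 1.0, the mean variance is 1.273, k = 1/1.273 = 0.785, and alpha ≈ 2.7%. A short simulation with a similar fall (100 trials) gave 4% and 5%. Its Monte Carlo SE is about 2 points, too large to confirm or contradict 2.7%.

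**Structures with visit-specific variances.** At 1.5-fold growth with 10% dropout, heterogeneous AR(1) gave 5.0% (400 trials, SE about 1.1 points) and unstructured gave 4.0% (150 trials, SE about 1.6 points).

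**The case against.** The strongest reply is that the plan already contains a guard. Heterogeneous AR(1) comes before the equal-variance structures, allows the Week 24 variance to differ, and held about 5% in the check. Two successive convergence failures are needed before the problem arises. In 1,211 simulated trials of this model (steepest litre path above, 10% or 20% dropout assumed), neither unstructured nor heterogeneous AR(1) failed once, although the data were normal and the optimiser was not the plan's Newton-Raphson. Even if both failed in 1% of trials (assumed), the overall error would be only 0.99 × 5% + 0.01 × 9% = 5.04% to 0.99 × 5% + 0.01 × 12% = 5.07%. This stands, and it keeps the point minor.

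It is also fair that the direction is not documented. A reader might infer that the SD of change is largest at Week 24. Nothing in the visible text says so, and the relevant quantity is the residual SD after covariate adjustment, not the raw SD. A reader might also object that AR(1) treats the 2-week and 12-week gaps as equal. Heterogeneous AR(1) and heterogeneous Toeplitz share that property, so it is no reason to prefer the list proposed here.

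Finally, the redacted text could specify a robust variance, so the criticism is limited to what is visible. What remains is that a rule written for the case of failure should hold its level when it is used, and the last two steps do so only if the Week 24 variance is close to the visit average.

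**Conclusion.** A minor point that holds conditionally. If both unstructured and heterogeneous AR(1) fail, the remaining steps test Week 24 with a variance pooled over Weeks 2-24. The type I error is then about 5% with constant SD, 7-8.5% at 1.2-fold growth, 9-12% at roughly 1.3- to 1.75-fold depending on the path, 12-17% if the SD doubles, and about 2.7% if it falls from 1.25 to 1.0. Some paths fall outside the middle band: 1.3-fold growth linear by visit gives 8.2%, and 1.75-fold linear by week gives 14.5%.

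A reader might infer that the primary analysis as planned runs at 9-12%. The documents do not support that. The planned analysis is unstructured, the first fallback allows visit-specific variances, and no SD pattern is given. The figures rest on assumed SD paths, normal data, Satterthwaite in place of Kenward-Roger, and no sandwich variance behind the redaction. The constant-SD simulations ran up to about 1 point above 5%, so differences of that size should not be over-read.

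**What to change.** In SAP Section 7.2.1, and before database lock, replace the fallback list by heterogeneous Toeplitz, then heterogeneous AR(1), then heterogeneous compound symmetry, all with Kenward-Roger. Delete homogeneous AR(1) and compound symmetry. Heterogeneous Toeplitz and heterogeneous compound symmetry were not simulated here; the case for them is that they estimate a Week 24-specific variance.

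If none converges, use an ANCOVA of the Week 24 change with the same baseline covariates. This also supplies a final step, which the visible text lacks.

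The cost is SAP wording. The ANCOVA has a small downside: it omits patients without a Week 24 value, so it loses some precision and gives up the MMRM's use of their earlier visits under MAR (SAP Section 7.2.1.1). The SAP should state that trade-off beside the rule.
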